The purpose of this study is to examine the impact of applying a capsaicin-based cream to the skin on human thermoregulation and thermal perception during exercise in the heat. The capsaicin chemical compound is found in many hot sauces, making it strongly associated with feelings of heat and pain. Topical capsaicin receptors can invoke a tingling sensation that can be perceived as heat. The capsaicin receptor is a part of a family of membrane proteins called transient receptor potential (TRP) channels [1]. TRPs allow for the perception of environmental stimuli and act as sensory mediators. The capsaicin receptor in our body, also known as vanilloid receptor one, is a TRPV1 channel. Besides activation of the TRPV1 channel by capsaicin, it is also activated by ambient noxious heat [1,3]. Capsaicin activated TRPV1 receptors lead to vasodilation of the skin [1]. This vasodilation is vital to the cooling of the body, as it gets rid of excess heat, aiding in thermoregulation. This can be contradictory to the perceived heat since it aids in cooling. It was first discovered that TRPV1 plays a role in thermoregulation when it was found that capsaicin has hypothermic action that can lower core temperature significantly in multiple species, including humans [2]. This evidence supported that TRPV1 has profound effects on maintaining homeostasis of internal body temperature.

If topical capsaicin provokes vasodilation, then the question remains as to why it is not more commonly used by humans in hot environments. This could be because of the previously referenced negative feelings of capsaicin. Currently, topical capsaicin creams are marketed as an analgesic, commonly aimed at those experiencing arthritic pains; yet this is not their full physiological potential. There is a physiological conflict between the perceived hot sensation of capsaicin compared to the observed physiological effects. It is currently unknown if over-the-counter capsaicin creams can aid in performance during exercise in the heat, or if the perceived burning sensation would hinder

performance. This requires further investigation into the effects that topical capsaicin may have on exercise performance in the heat.

Participants

12-15 subjects, aged 19 to 45, will be needed to complete the study. Keeping the age range of 19-45 ensures that the participants will be of consenting age and cleared for physical activity participation.

Research Plan

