Following instrumentation, subjects will sit for 5 minutes as a baseline for all recordings in a temperate environment. Immediately after, a researcher with gloved hands will topically apply capsaicin or the control hypoallergenic cream from the shoulder to wrist and mid-thigh to ankle. Subjects will then enter the heat chamber (38°C, 60% relative humidity) and immediately begin a 30-minute walk on a treadmill (3.5 mph, 5% grade). Subjects will be intermittently asked to hold their arm steady for laser doppler flow collection (10, 20, 30 minutes). Subjects will also briefly pause at minute 10 in order to adhere an absorbent patch to their forehead for sweat collection over the following 10-20 minutes. Thermal perception using the ASHRAE scale (cold to hot) will be assessed pre and during exercise. After 30 minutes of walking, subjects will exit the chamber for removal of all skin and finger sensors. Subjects will then re-enter the private room, remove their own rectal thermistor with gloved hands, and then a final nude body weight will be recorded after toweling off.

The rectal thermistor will measure core temperature. The heart rate monitor will measure the beats of the heart. Skin thermistors will measure the temperature of the skin surfaces. Laser doppler flow measure the relative units of blood flow velocity. Galvanic skin response measures skin conductivity changes as individuals begin to sweat. Sweat is collected for assessment of sweat composition. Thermal perception is assessed for individual perception surrounding the temperature of the ambient environment. Nude body weight is measured to calculate sweat rate.

Statistical Analysis

Recruitment

Previous exercise research suggests that the difference in response of matched pairs is normally distributed with a standard deviation of 0.86. If the true difference of the mean response of matched pairs is 0.75, we will need to complete 12 experimental trials for each condition to be able to reject the null hypothesis that this response difference is zero with a power of 0.8. The Type I error probability associated with this test of the null hypothesis is 0.05.

Interventions

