A repeated measures two-way ANOVA (Time x condition) will be used for the dependent variables. If the F-ratio values are found to be significant, a Fisher's Least Significant Difference post hoc analysis will be conducted. A type I error probability of < 5% will be considered significant ($p < 0.05$). All data will be analyzed using a combination of Microsoft Excel and the Statistical Package for the Social Sciences (SPSS).

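### The sample size rests on one paired difference tied to no outcome, while about eight outcomes are each tested at 0.05 with no primary outcome and no adjustment across them

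*Combined protocol and SAP*

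**What the plan says.** Under Statistical Analysis, Recruitment, the study is sized on a single matched-pair comparison: "Previous exercise research suggests that the difference in response of matched pairs is normally distributed with a standard deviation of 0.86". The paragraph continues "If the true difference of the mean response of matched pairs is 0.75" and arrives at 12 trials per condition, with power 0.8 and a Type I error of 0.05 attached to that one test. It gives no outcome, unit, time point or sidedness. The Participants section gives the target as "12-15 subjects, aged 19 to 45, will be needed to complete the study".

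Under Statistical Analysis, Interventions, the analysis is "A repeated measures two-way ANOVA (Time x condition) will be used for the dependent variables". Fisher's LSD follows a significant F, and "A type I error probability of < 5% will be considered significant". No outcome is singled out, and nothing is said about error across outcomes.

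The Abstract, Research Plan and Experimental Visits 2 and 3 between them list eight outcomes: core temperature, skin temperature, heart rate, laser Doppler flow, galvanic skin response, thermal sensation, sweat rate and sweat composition.

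**The concern.** A power statement is useful only if the reader knows which test it describes. Here it cannot be worked out. The outcomes are on different scales (temperature, heart rate, relative flow units, conductance, a rating scale, body weight), and 0.75 with SD 0.86 carries no unit.

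The analysis paragraph does not resolve this. It does not say whether the condition F or the interaction F answers the question, or which times form the Time factor. Minutes 10, 20 and 30 are specified only for laser Doppler flow. This matters because the cream goes on after the resting baseline: "Immediately after, a researcher with gloved hands will topically apply capsaicin or the control hypoallergenic cream". If that baseline is a level of Time, the condition main effect averages in a value taken before any treatment, and the interaction carries much of the signal. If it is left out, the condition main effect is the natural test.

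Two things are at stake. With about eight outcomes at an unadjusted 0.05 and none given priority, an isolated significant result is much easier to obtain by chance than the single-test 5% suggests. And a null result cannot be read against a detectable effect in natural units for a named outcome.

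**Working it through.** **1. The plan's own figure.** Inputs from Recruitment: difference 0.75, SD of paired differences 0.86, alpha 0.05, power 0.80, 12 pairs. Assumption: two-sided testing, the natural reading of a null of zero difference.

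- Standardised difference: 0.75 / 0.86 = 0.872.
- Noncentrality at n = 12: 0.872 x √12 = 3.02, on 11 degrees of freedom.
- Power from the noncentral t distribution: 78.5% at 12 pairs, 82.3% at 13, 88.1% at 15.
- Smallest n reaching 80%: 13. The normal approximation gives (0.86 x (1.960 + 0.842) / 0.75)² = 10.3, so 11 pairs.
- One-sided testing would give 88.2% at 12.

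Twelve is therefore approximately right for one two-sided paired test.

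**2. What that size can detect.** At 80% power and two-sided 0.05, the detectable difference is 0.889 SD at n = 12, 0.847 SD at 13 and 0.778 SD at 15. Multiplied by 0.86, these are 0.764, 0.728 and 0.669 in the plan's unnamed unit. Conversely, a difference of 0.75 keeps 80% power only if the SD of the chosen contrast is at most 0.75 / 0.889 = 0.84 at n = 12, or 0.75 / 0.778 = 0.96 at n = 15. With an SD of 1.0 (assumed, for illustration), power is 65.8% at 12 and 77.1% at 15.

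**3. Number of outcomes.** Eight, as listed above. The three skin sites (chest, forearm, calf) count as one, and so does sweat composition.

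**4. Error across outcomes.** Assume no true effect on any of the eight, and one condition test per outcome at 0.05. With two conditions, the condition F is the square of a paired t on each participant's time average, so each test can be treated as a paired t on 12 pairs.

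- Independent outcomes: 1 − 0.95^8 = 1 − 0.663 = 33.7%.
- Equally correlated outcomes, by simulation with 12 pairs: about 31% at correlation 0.3, 26% at 0.5 and 17% at 0.8. The documents give no correlations, so these are assumed.
- Sensitivity to the count, if independent: 22.6% for five outcomes and 40.1% for ten.

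**5. Does the post hoc gate help?** Fisher's LSD is used only after a significant F, but that gate operates within one outcome. It does not affect the chance that at least one of eight F tests is significant.

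**6. Does the model fit every outcome?** For sweat composition, "Subjects will also briefly pause at minute 10 in order to adhere an absorbent patch to their forehead", with collection over the following 10 to 20 minutes. That is a single collection window per visit, so there is no Time factor and a Time x condition ANOVA cannot be fitted to it.

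**The case against.** The strongest reply is that this is a small physiological crossover study that sets out to examine thermoregulation and thermal perception, which are separate questions. The plan states no rule that any one significant outcome establishes a capsaicin effect. That is correct: a reader might infer such a rule, but it is not written. What stands is narrower. The plan attaches power and a Type I error to one test, does not identify it, and then gives every outcome the same unadjusted threshold.

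Other stronger readings also go beyond the documents:

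- **The sample size is wrong.** It is not, for one paired test. The gap between 78.5% and 80% is trivial.
- **The planned ANOVA is underpowered.** This cannot be shown. Its power depends on which times enter, their correlation and the shape of the effect, none of which the plan gives.
- **A null result cannot be interpreted at all.** Too strong. The detectable effect of 0.889 SD at n = 12 applies to a paired contrast on any outcome, and confidence intervals would also inform a null result. What is missing is the link to a named outcome in its own unit.
- **Sweat rate does not fit the ANOVA either.** The plan says "Nude body weight is measured to calculate sweat rate". A two-by-two analysis of weight before and after exercise gives, through its interaction F, the same test as a paired contrast on weight loss.
- **The trial has no primary outcome.** A primary may be set elsewhere. The point is only that this document does not name one.

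The outcomes are probably correlated, which lowers the error across them, but even at an assumed correlation of 0.8 it is about 17%.

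**Conclusion.** The point holds in this limited form. The 80% power and 5% error describe one paired difference with no outcome, unit or time point, whereas the analysis tests about eight outcomes at 0.05 each without a primary, a deciding F or adjustment. If all eight are null, the chance of at least one false positive is 34% under independence and about 26% or 17% at correlations of 0.5 or 0.8. These figures rest on a count of eight, one condition test per outcome and the assumed correlations. They describe the error rate across the set and do not show that any particular result will be false. The design is not invalidated and the number 12 is not in error. The paragraph should be corrected before the data are analysed.

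**What to change.** Before analysis:

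1. Name one primary outcome, with its unit and time point, and one capsaicin-minus-control paired contrast tested once at two-sided 0.05. The change from the pre-cream baseline to minute 30 is one example. The choice of outcome is the sponsor's. If a primary is already set elsewhere, copy it here.
2. State whether 0.75 and 0.86 are the mean and SD of that same contrast. If they are, restate power as about 78.5% at 12 completers, 82% at 13 and 88% at 15, two-sided. If not, report the power that 12 to 15 completers give with the right SD.
3. Label all other outcomes secondary and report them as estimates with 95% confidence intervals.
4. Analyse sweat composition with a paired contrast between visits.

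The cost is a rewritten statistics paragraph. Naming a primary does not itself require more participants. If 0.75 and 0.86 apply, 80% power needs 13 completers, within the planned range. If the contrast's SD were 1.0 (assumed), it would need 16, and the sponsor would have to recruit more or report the lower power. The alternative, a Bonferroni split over eight outcomes at 0.05 / 8 = 0.00625, costs far more: at 0.75 and 0.86, power falls to 41.4% at 12 and 57.7% at 15, and 80% needs 21 pairs. The downside of the recommended route is that the other outcomes become supportive only, and the stated power may fall slightly below 80%.

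### The plan has no missing-data rule for a repeated measures ANOVA that conventionally uses complete cases only; a mixed model on all readings obtained should replace it

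*Combined protocol and SAP*

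**What the plan says.** One method is given for every outcome, in the Interventions part of the Statistical Analysis section: "A repeated measures two-way ANOVA (Time x condition) will be used for the dependent variables". The software sentence reads "All data will be analyzed using a combination of Microsoft Excel and the Statistical Package for the Social Sciences (SPSS". It does not say whether GLM Repeated Measures or MIXED is meant.

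The only analysis times stated anywhere are those for skin blood flow, under Experimental Visits 2 and 3: "Subjects will be intermittently asked to hold their arm steady for laser doppler flow collection (10, 20, 30 minutes". Core temperature, skin temperature, skin conductance and heart rate are recorded continuously, and the points to be taken from them are not stated.

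The Recruitment part sizes the trial on a paired difference that is "normally distributed with a standard deviation of 0.86". It continues "If the true difference of the mean response of matched pairs is 0.75", "we will need to complete 12 experimental trials for each condition" "with a power of 0.8", and adds "The Type I error probability associated with this test of the null hypothesis is 0.05". The Participants section asks for 12 to 15 subjects to complete.

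No section gives a rule for missing readings, an analysis population, an expected loss rate, or the handling of data from a walk that ends before 30 minutes.

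**The concern.** A conventional repeated measures ANOVA needs every condition-by-time cell for each person. If one analysed cell is empty at one visit, the person leaves that outcome's analysis at both visits, and the readings that were obtained are discarded. Sensors are taped or strapped to people who are walking and sweating at 38°C and 60% relative humidity, and the Doppler readings depend on a still arm at three moments. Anyone who stops early has no minute-30 cell for any outcome analysed over time.

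Two things are at stake. The first is power, because the calculated 12 has no allowance for loss. The second is selection: if those who stop early are those under most strain at that visit, the people left in the analysis have been selected on the outcome. Recruiting more participants restores the number but not the people selectively lost.

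**Working it through.** **Inputs.** From the Recruitment part: mean paired difference 0.75, SD of differences 0.86, alpha 0.05, power 0.80, 12 completed trials per condition. Sidedness is not stated; two-sided is assumed from the null of zero difference. Standardised effect: 0.75/0.86 = 0.872.

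**The plan's own figure.** Normal approximation: n = (0.86 × (1.960 + 0.842)/0.75)² = 10.3, rounded up to 11. Exact paired t (noncentrality 0.872 × √n, n − 1 degrees of freedom): power 78.5% at 12 and 82.3% at 13. The stated 12 lies between the two answers and is reproduced to within rounding of method.

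**Power by number of complete pairs (exact, two-sided).**

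| Complete pairs | 9 | 10 | 11 | 12 | 13 | 14 | 15 |
|---|---|---|---|---|---|---|---|
| Power | 63.2% | 69.0% | 74.1% | 78.5% | 82.3% | 85.4% | 88.1% |

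Starting from 12, each person lost costs about 4 to 6 points.

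**Loss under complete-case deletion.** With m analysed cells per person and an independent chance q that a cell is empty, the share of people dropped is 1 − (1 − q)^m. Three Doppler times over two visits give m = 6; adding baseline gives m = 8. The documents give no value for q, so 1% to 5% is an assumed range. Power is averaged over the binomial number of complete cases.

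| m | q | Dropped | From 12: complete cases, power | From 15: complete cases, power |
|---|---|---|---|---|
| 6 | 1% | 5.9% | 11.3, 75.3% | 14.1, 85.6% |
| 6 | 2% | 11.4% | 10.6, 71.9% | 13.3, 82.8% |
| 6 | 5% | 26.5% | 8.8, 61.1% | 11.0, 73.2% |
| 8 | 1% | 7.7% | 11.1, 74.2% | 13.8, 84.7% |
| 8 | 2% | 14.9% | 10.2, 69.6% | 12.8, 80.8% |
| 8 | 5% | 33.7% | 8.0, 55.3% | 9.9, 67.5% |

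Keeping partial records would hold power for 12 participants between the reduced-n value and 78.5%. All of this is for the paired contrast. Power for the time-by-condition interaction cannot be computed, because no within-person correlations or time profile are given.

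**Selection (illustration only).** Simulated pairs had a true difference of 0.75 and an SD of differences of 0.86. Anyone whose higher visit value passed a threshold was removed, with the threshold set to lose 5%, 13% or 26% of people.

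| Between-person SD (assumed) | 5% lost | 13% lost | 26% lost |
|---|---|---|---|
| 0.3 | 0.70 | 0.64 | 0.57 |
| 1.0 | 0.72 | 0.70 | 0.66 |
| 2.0 | 0.74 | 0.72 | 0.70 |

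If loss depends only on a person's general heat tolerance and not on strain at that visit, the estimate stays at 0.75.

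**Why the replacement model needs a visit-level term.** Data were simulated with no condition effect, for 12 people and 4 times per visit. A model with a participant intercept alone rejected in about 14% to 27% of trials when the participant-by-condition SD was 0.5 to 1.0 times the residual SD. With the correct error term it rejected in about 5%.

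**The case against.** A reader might infer that the plan drops anyone with any missing reading. The documents do not say that. They name a class of model and a software package, and SPSS also offers MIXED. Exclusion is the default of the conventional procedure, and the defect in the text is silence on the matter.

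Nor would any lost reading have this effect. Deletion works per outcome and per analysed cell. A brief gap in a continuous signal need not empty a cell. Skin temperature is taken at three sites, and how they are combined is not stated. Sweat rate is one value per visit from body weight. The concern fits Doppler best, and perhaps thermal sensation, whose times during exercise are not given.

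A reader might also infer that missing data are what takes power below 80%. Power is already 78.5% at 12 with nothing missing. Both the 12 and the 12 to 15 are counts of completers, and with 15 participants even the 8-cell, 2% case keeps about 81%.

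Finally, the documents neither report nor anticipate early stopping, and participants are screened for exercise readiness before a moderate 30-minute walk. Bias toward no effect is therefore a conditional risk.

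These points narrow the concern and all of them stand. They do not supply the missing rule, and the range up to 15 is not tied to any expected loss.

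**Conclusion.** The concern holds in a limited form: the plan pairs a method that conventionally uses complete cases with no missing-data rule, in a crossover with at most three participants above its calculated 12. Losing one or two from 12 takes power to 74.1% or 69.0% on the plan's inputs, assuming a two-sided test. With 15 participants, an assumed 1% to 2% of empty cells is absorbed (about 81% to 86%), while 5% is not (67.5% to 73.2%).

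The documents do not support the stronger conclusion that the result will be biased toward no effect. That needs stopping related to strain at that visit, and its size rests on a between-person SD and a loss rate that are not given. This merits a change to the analysis plan; it does not undermine the design.

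**What to change.** Replace the ANOVA, for outcomes measured over time, with a linear mixed model in SPSS MIXED that uses every reading obtained, including those before an early stop. Specify:

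- fixed effects for condition, time, condition-by-time and visit order;
- random effects for participant and for participant-by-condition (that is, visit), or an equivalent prespecified within-visit covariance, because a participant intercept alone makes the condition test anti-conservative;
- REML with small-sample degrees of freedom, such as Satterthwaite;
- the time points to be analysed for each outcome, and what makes a cell missing for a continuous signal;
- the complete-case ANOVA as a sensitivity analysis;
- the number and timing of early stops, by condition.

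The cost is plan wording and a different menu in software already named. There are two limits: the covariance structure must be fixed in advance, and the model is valid only if missingness depends on observed readings, so it reduces the selection problem without guaranteeing its removal.
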